4.4 Locator/Contact Information

At the end of the screening questionnaire, interested and eligible individuals will be asked to provide their preferred method of contact and an alternative method of contact. A method of contact may be an email address, phone number, or Facebook profile name. Participants will review a sample voice/text message, and then asked if such messages can be sent (via SMS) and/or left (voicemail) via their preferred contact information. RS will only send/leave messages if expressly permitted to do so. Contact information will be accessible by designated research staff at the relevant research site, as well as the data manager, Program Manager, and the PI. All contact information will be stored in the “Scheduling Log”, which is separated from the study visit data. IU researchers will have access to the scheduling log for monitoring purposes.

4.5 Informed Consent

After a screened participant is determined to be eligible, s/he will receive a study information sheet and provide verbal consent for the study. The study details will be discussed and all questions answered during the informed consent process. Written consent is not required, since this would include the only identifying information for participants in the study. Minors will not require parental consent to participate. Verbal informed consent from the individuals as determined by local Institutional Review Boards (IRB) will be obtained before any study related procedures are performed. Enrollment will occur after participant consent is obtained.

Those individuals who refuse to provide verbal consent to participate in the study will be asked if they are willing to provide their reason for declining participation and if answered; the responses will be recorded in an anonymous manner on the screening questionnaire.

4.6 Co-enrollment Guidelines

Co-enrollment in other clinical studies is allowed and approval from the Protocol Team for co-enrollment is not required.

5.0 STUDY PROCEDURES

A Schedule of Evaluations, located in Appendix 1, provides a timeline for each study activity.

5.1 Enrollment Procedures

Enrollment and study completion will occur on the same visit. Participants who are confirmed eligible and complete the consent process will immediately begin the study procedures. The participant will be considered enrolled after they provide verbal consent.

5.2 Randomization Procedures

5.2.1. Adolescent Participants

Adolescents will be randomized in a 1:1:1 ratio into 1 of the 3 consent conditions using block randomization with block size k=3 (so that in every 3 subjects, exactly 1 is allocated to each condition). The randomization will be stratified by study site and sex assigned at birth. Within study site, sex assigned at birth, and consent condition, the order in which the hypothetical trials will be presented to adolescents will be block randomized with block size k=2.

A subset of 6-8 adolescents (3-4 of both sexes) at each site will be selected using quota sampling for participation in the debriefing interview. Participants will be asked if they are willing to participate in the debriefing interview unless the quota for their demographic group has been reached.

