Potential participants will be recruited from clinical settings and HIV testing centers, or self-screen online. Potential participants will take a short CASI screening survey to determine eligibility. All eligible participants will provide contact information to establish a study visit appointment. Those eligible and screening in-person will either participate on the same day as the screening, or, if unable to stay, they will be contacted to establish a study visit appointment. Eligible participants who screen online will also provide their contact information to establish a study visit appointment.

Study participants will attend an in-person session at their respective AMTU. During the session, they will complete a CASI that collects demographic, social, behavioral, and attitudinal measures.

All study participants will undergo a simulated consent process for each of two hypothetical studies modeled after ATN 113 and HPTN 077. Procedures are slightly different for parents than for adolescents, so each group is described separately below:

Adolescent Participants: First, the adolescent participant will complete a demographic CASI. *For each hypothetical trial*, RS will lead the participant through a simulated consent process consistent with their randomized consent condition. Then, the participant will complete a CASI assessing WTP and will work with RS to complete the UCSD Brief Assessment of Capacity to Consent (UBACC). After the second UBACC, the adolescent will complete overall WTP, medical mistrust, and end of study questions.

Parent Participants: *For each hypothetical trial*, RS will review the informed consent forms with the parent. The parent will complete a CASI with three vignettes that describe each of the three possible consent conditions. Parents will rate the acceptability of each vignette. Then, the participant will work with RS to complete the UCSD Brief Assessment of Capacity to Consent (UBACC). After the second UBACC, the participant will answer demographic questions, medical mistrust, and end of study questions.

A subset of 6-8 adolescents and 6-8 parents per study site will complete a debriefing interview assessing adolescent and parent perspectives on the various consent conditions in greater depth, and to better understand the role of study features, family, and adolescent characteristics in willingness to

participate/willingness to support the hypothetical research studies.

MONITORING:

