3.2 Sample Size

This study will enroll approximately 144 (36 per study site) high-risk minor adolescents and 144 (36 per study site) parents of adolescents. A subset of 24-32 (6-8 per study site) adolescents and 24-32 (6-8 per study site) parents will be selected to participate in the debriefing interview. Of note, the adolescents and parents will not be parent-child dyads; they will be unrelated. We project total enrollment of 288 participants, however, since this is a multi-site project with simultaneous recruitment with a hard to reach population, we may schedule and enroll more subjects than anticipated.

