3.3 Study Randomization, Stratification, or Description of Non-Random Assignment Procedures

Adolescents will be randomized in a 1:1:1 ratio into 1 of the 3 consent conditions using block randomization with block size k=3 (so that in every 3 subjects, exactly 1 is allocated to each condition). The randomization will be stratified by study site and sex assigned at birth. Within study site, sex assigned at birth, and consent condition, the order in which the hypothetical trials will be presented to adolescents will be block randomized with block size k=2.

Enrollment of parents will be restricted to approximately 15 parents of adolescent natal males and 15 parents of natal adolescent females at each study site. Parents will indicate the acceptability of each of the three consent conditions for each of the two hypothetical trials. Independently of the gender strata, the order of hypothetical trial presentation will be block randomized with blocks size k=2. Separately for each hypothetical trial, the order of evaluation for the three consent conditions will be randomized so that each ordering is equally likely.

A subset of 6-8 adolescents (3-4 natal males and 3-4 natal females) and 6-8 parents of adolescents (3-4 parents of natal males and 3-4 parents of natal females) at each site will be selected for participation in the debriefing interview. All study participants will be asked if they are willing to participate in the debriefing interview until quotas have been reached.

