To avoid the accidental inclusion of parent-child dyads, we will ask each participant to give the first 5 digits of their street address and first 4 characters of apartment/unit, where applicable. For example, if someone lived at 1234 Main Street Apt. 408, the value for that address would be 01234408. The value will be labeled “Family ID” and stored only until the end of the enrollment period. Once the site has filled all quotas, the Family ID will be permanently deleted. The RS will receive an email from Qualtrics indicating the participant’s eligibility. If the participant is eligible based on the screening questionnaire, the RS will use the Family ID Report in Qualtrics to identify any matching Family IDs. If there is no match, the participant qualifies and can begin the study. All eligibility requirements are assessed without the PI’s input. If interested, the adolescent will either: 1) provide contact information to arrange the study visit or 2) complete the study procedures the same day as s/he was screened. Eligible participants will be invited to participate in an on-site debriefing interview (until quota is filled), immediately following the final CASI.

4.3.2 Parents or guardians:

This study will recruit 36 parents/guardians at each site. Parents will be recruited primarily through contact in the clinical setting. If recruitment is slow, we will begin using advertising on social media (Facebook, Twitter), the LGBTQ youth centers referenced above, and through the local chapters of Parents, Families, and Friends of Lesbians and Gays, as well as churches, and other social settings familiar to our target audience. Parents recruited in person will complete the questionnaire on a tablet on the same day they are recruited. Parents who self-refer or hear about the study from friends will need to complete the screening questionnaire online.

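### The fixed block of 3 within site-by-sex strata lets staff who track allocations know up to one third of adolescent allocations in advance

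*Combined protocol and SAP*

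**What the plan says.** Section 5.2.1 gives the adolescent scheme: "Adolescents will be randomized in a 1:1:1 ratio into 1 of the 3 consent conditions". The method for doing so is described there as "using block randomization with block size k=3 (so that in every 3 subjects, exactly 1 is allocated to each condition". On strata, the section adds: "The randomization will be stratified by study site and sex assigned at birth". The Study Abstract and Section 3.3 print the same fixed size ("block randomization with block size k=3"). Presentation order is blocked too: "the order in which the hypothetical trials will be presented to adolescents will be block randomized with block size k=2".

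On staff roles, the Study Abstract says that for each hypothetical trial "RS will lead the participant through a simulated consent process consistent with their randomized consent condition", and Section 5.3 has the same staff go through the condition-specific form. Sections 8.1 and 11.1 give research staff the task of contacting and rescheduling eligible people. Section 4.3.1 lets an eligible adolescent either arrange a later visit or "complete the study procedures the same day as s/he was screened".

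Two features limit discretion. The survey software decides eligibility (Section 6.1), and procedures begin directly after verbal consent (Section 5.1). The documents do not mention varying block sizes or allocation concealment. They do not say who generates or holds the list, or when an allocation is released.

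**The concern.** Three is the smallest block possible for a 1:1:1 allocation to three conditions, and its size is printed in the protocol that sites follow. Once two adolescents in a block have been allocated, the third condition is fixed. Staff who delivered the first two conditions can work it out before they approach or book the next person of that sex.

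Automated eligibility does not remove this foreknowledge. The software does not choose whom staff approach in clinic, which is the main recruitment route (Sections 3.1 and 4.3.1), when a visit takes place, or how hard a missed visit is pursued beyond the minimum of three attempts (Section 8.1). Starting procedures straight after consent limits changes after enrolment, but selection would happen before it.

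The comparison at stake is the primary one for Aim 1, willingness to participate (WTP) across the three conditions. Section 1.1 presents forced disclosure to parents as the reason why a parental-permission requirement deters adolescents. Openness with parents is therefore a plausible prognostic factor under that condition. The primary model in Section 10.4.1 contains condition, trial type, sex and site. Family context enters only a secondary sensitivity analysis, so an imbalance in it would pass into the primary estimate.

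**Working it through.** **Inputs.** Three conditions, 1:1:1, fixed block of 3 (Sections 3.3 and 5.2.1). Four sites by two sexes = 8 strata. Section 3.2: "This study will enroll approximately 144 (36 per study site) high-risk minor adolescents". No sex split is stated for adolescents.

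**The plan's own figure.** The plan gives no predictability figure. Its only computed design figure is 80% power at f² = 0.09 with 120 participants and 7 predictors (Section 10.3). A noncentral F with 2 and 120 − 7 − 1 = 112 degrees of freedom and λ = 0.09 × (2 + 112 + 1) = 10.35 gives 81.9%. The effect detectable at 80% is f² = 0.086, which rounds to 0.09, so the figure reproduces. The present point does not depend on it.

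**Step 1: one complete block.** A person who knows the earlier allocations guesses the first correctly with probability 1/3, the second with 1/2 and the third with 1.
- Share certain: 1/3 = 33.3%.
- Best-guess rate: (1/3 + 1/2 + 1)/3 = 61.1%, against 33.3% by chance.

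**Step 2: counts.** Each complete block yields one certain allocation. With 36 adolescents at a site:
- Split 18 + 18: 6 + 6 = 12 complete blocks, so 12 certain.
- Split 17 + 19: 5 + 6 = 11 complete blocks, so 11 certain.

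Every possible split gives 11 or 12. Over four sites that is 44 to 48 of 144, or 30.6% to 33.3%. With 11 complete blocks, the leftover places (two in one stratum, one in the other) give a best-guess rate of (11 × 11/6 + 1/3 + 1/2 + 1/3)/36 = 21.33/36 = 59.3%. So 61% is also a ceiling.

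**Step 3: alternatives.** Fixed blocks were enumerated exactly. Mixed blocks were simulated with equal probability for each size, 18 per stratum, and a guesser who knows the possible sizes and guesses optimally.

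| Scheme | Certain in advance | Of 144 | Best-guess rate |
|---|---|---|---|
| Fixed 3 (plan) | 33.3% | 48 | 61.1% |
| Fixed 6, size known | 20.0% | 29 | 56.1% |
| Fixed 9, size known | 14.3% | 21 | 53.2% |
| Random 3 and 6 | about 8% | about 11 | about 57% |
| Random 3, 6 and 9 | about 3% | about 4 | about 54% |

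**Step 4: where the gain lies.** With random 3 and 6, the excess over chance goes from 61.1 − 33.3 = 27.8 points to 57.0 − 33.3 = 23.7 points, so about 85% of it remains (23.7/27.8). The improvement is mainly in certain allocations, which fall by roughly three quarters, from 33.3% to about 8%.

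**Scope.** Each parent rates all three conditions, so the parent comparison is unaffected. The block of 2 for presentation order makes every second order within a site, sex and condition cell certain. Each adolescent sees both trials, so less depends on it.

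**The case against.** The strongest reply is that predicting an allocation is not the same as acting on it. Acting on it needs a choice among eligible adolescents of the same sex at that moment, in what Section 3.2 calls a hard-to-reach population. It also needs knowledge of their openness with parents. Screening collects eligibility items, an address code and contact details. Parental monitoring is measured only at the visit, after consent, on the participant's own screen (Sections 5.3 and 6.2). Staff have no evident motive: the trials are hypothetical, real participation needs no parental consent in any condition (Section 4.5), and payment is the same (Section 8.2). Small fixed blocks also keep close balance in strata of about 18. Release after consent may already be the practice, since the condition-specific form follows the first questionnaire.

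Much of this stands and keeps the point at the level of a cheap improvement. It does not remove the foreknowledge. Clinic staff may know families, and late release does not stop a prediction made from earlier allocations.

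A reader might infer more than the documents support:
- That research staff run the randomisation. The text shows only that they deliver the condition. Automated release would leave the predictability unchanged.
- That one third of allocations will in fact be known. This needs one person to know the earlier allocations in the stratum, and the number of staff per site is not given.
- That disclosure to parents is the main driver of WTP. Section 1.1 supports it as a concern and does not rank it.

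**Conclusion.** The point holds as a low-cost design improvement. Up to one third of adolescent allocations are certain, and up to 61% guessable, for staff who track them in an unblinded study with no described concealment. The figures assume about 144 adolescents, 36 per site, and full knowledge of earlier allocations in the stratum. The mixed-block figures further assume 18 per stratum and known possible sizes.

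The documents show an open route to selection bias in the Aim 1 contrast. They do not show that anyone would use it, and they give no basis for estimating the direction or size of a bias. It would be wrong to conclude that the Aim 1 result is biased.

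**What to change.** Within the same site-by-sex strata, replace the fixed block of 3 with randomly varying sizes, for example 3 and 6, or 3, 6 and 9. Remove the sizes from the Study Abstract and Sections 3.3 and 5.2.1 and hold them in a restricted randomisation file. State who generates and holds the list, and that each allocation is released only after verbal consent is recorded. Concealing the sizes should lower predictability below the simulated figures, by an amount not quantified here. The block of 2 for presentation order can be handled in the same way.

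The cost is a new allocation list and revised wording, with no change to sample size, visits or analysis. The downside is a possible imbalance of a few participants from incomplete last blocks. Within a stratum, two conditions could differ by up to 2 (block of 6) or 3 (block of 9), against 1 now.

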5.2.2. Parent Participants

Enrollment of parents will be restricted to approximately 18 parents of adolescent natal males and 18 parents of natal adolescent females at each study site. Parents will indicate the acceptability of each of the three consent conditions for each of the two hypothetical trials. Independently of the gender strata, the order of hypothetical trial presentation will be block randomized with blocks size k=2. Separately for each hypothetical trial, the order of evaluation for the three consent conditions will be randomized so that each ordering is equally likely.

A subset of 6-8 parents at each site will be selected using quota sampling for participation in the debriefing interview. Participants will be asked if they are willing to participate in the debriefing interview unless the quota for their demographic group has been reached.

5.3 Investigation Procedures

RS will prepare the participant's iPad for the beginning of the study visit. Adolescents will complete demographic, social, and attitudinal measures by CASI. Once completed, RS will begin

the simulated consent process for study 1 or study 2 (depending on randomization) by reviewing the hypothetical consent form (which reflects the randomly assigned consent condition; Appendix II). RS will allow time for questions about the hypothetical study from the participant, provide answers as needed. The RS will then ask the adolescent to complete the WTP questions on their iPad. Finally, the RS will administer the UCSD Brief Assessment of Capacity to Consent (UBACC)²⁵ for study 1 or study 2 (depending on randomization). The RS will then repeat the simulated consent process, WTP, and UBACC for the additional hypothetical study (study 1 or study 2 depending on randomization).

For parent participants, RS will prepare the participant's iPad for the beginning of the study visit. RS will begin the simulated consent process for study 1 or study 2 (depending on randomization) by reviewing the hypothetical consent form (which reflects the randomly assigned consent condition; Appendix II). RS will allow time for questions about the hypothetical study from the participant, provide answers as needed. The RS will then ask the parent to read the vignettes and answer WTS questions on their iPad. Finally, the RS will administer the UCSD Brief Assessment of Capacity to Consent (UBACC)²⁵ for study 1 or study 2 (depending on randomization). The RS will then repeat the simulated consent process, vignettes and answer WTS questions, and UBACC for the last hypothetical study (study 1 or study 2 depending on randomization). Parents will then complete demographic, social, and attitudinal measures by CASI.

For both adolescent and parent participants, after all data are collected and saved, the RS will determine whether the participant is eligible to participate in the debriefing interview. Eligibility is determined by quota (3-4 natal male adolescents and 3-4 natal female adolescents at each site; 3-4 parents of adolescent natal males and 3-4 parents of adolescent natal females at each site). If the quota is not filled, the participant will answer a question at the end of the Qualtrics survey asking if they would like to participate in a debriefing interview. If quota is filled, the RS for that site will be notified and IU will remove the question from Qualtrics.

The participants will complete all CASIs using Qualtrics database via a provided iPad.

The RS will verbally administer the UBACCs. UBACCs and debriefing interviews will be audio recorded with participants permission.

5.4 RS Training

Interview RS training, intervention monitoring, and quality control (section 5.5) will be done by [name] and the Consent 2.0 Program Manager. RS conducting the interviews will ideally have some experience with open-ended questioning and interviewing (e.g., HIV counseling, anthropology, psychology, nursing, social work); however, experience is not absolutely necessary, and an individual with good listening and interpersonal skills can be trained in the technique.

[name] will visit each research site to conduct initial RS training over the course of two days. The two day training will cover:

- Background and rationale for project
- Project goals

- Work with human subjects, with special attention to issues of adolescent consent to biomedical HIV prevention research
- Overview of the two hypothetical research studies
- Overview of all study instruments
- Practice interviewing, using actual study instruments
- Debriefing of practice interviews to identify areas of improvement
- Writing field notes
- Dealing with participant disclosures
- Directed reading on qualitative techniques

Practice interviews will focus on self-presentation, and specific interview techniques, such as active listening, use of silence, avoiding leading questions, outlining, summarizing, and tabling (when the adolescent participant brings up two interesting concepts, tabling one and pursuing the other).

5.5 Monitoring/Quality Control

Monitoring and quality control for the debriefing interviews will be done by a qualitative research team consisting of [name] and the Consent 2.0 Program Manager.

Quality of CASI and debriefing interviews will be intensely monitored at the start, and then periodically by the qualitative research team. After each of the first three interviews at each site, and before the fourth interview takes place, the qualitative research team will listen to the interview. Together, they will discuss the interview, covering (1) interview technique (good and bad), (2) interview content, (3) techniques to practice in the next interview, and (4) areas for further inquiry.

After listening to the first several together, a subset of subsequent interviews will be listened to by the qualitative research team. These will be identified by either the RS or the qualitative research team, and include interviews that went particularly well or particularly poorly, or interviews with interesting content.

